A Phase II Clinical Study of First-Line Immunotherapy Combined with Chemotherapy for Advanced Small Cell Lung Cancer

Study Protocol

Protocol Number: Version Number: 1.1

Date of Document: January 7, 2021

Clinical Trial Sponsoring Organization: Shanghai Pulmonary Hospital Clinical Trial Data Statistics Organization:

Clinical Trial Applicant Organization: Shanghai Pulmonary Hospital

Protocol Summary

Study Title	A Phase II Clinical Study of First-Line Immunotherapy Combined with Chemotherapy for Advanced Small Cell Lung Cancer
Study Number	
Version Number	1.1
Responsible Organization	Shanghai Pulmonary Hospital
Principal Investigator	[name]
Study Subjects	Patients with Advanced (Extensive-Stage) Small Cell Lung Cancer
Purpose of the Study	 Main Objective: To evaluate the 1-year Progression-Free Survival (PFS) rate of subjects receiving first-line treatment with PD-1 inhibitor combined with chemotherapy. Secondary Objectives: To assess Progression-Free Survival (PFS), Overall Survival (OS), and Objective Response Rate (ORR) of subjects according to RECIST 1.1; To evaluate the quality of life of subjects based on the EORTC QLQ-C30 scoring; To assess the incidence of adverse events (AEs) in subjects. Exploratory Objectives: To identify potential predictive biomarkers for the efficacy of immunotherapy in the treatment of advanced (extensive-stage) small cell lung cancer.
Study Design	This study is a single-center, prospective, single-arm, open-label Phase II clinical study to observe the efficacy and safety of Sintilimab combined with chemotherapy in previously untreated extensive-stage small cell lung cancer (SCLC) subjects. The trial plans to enroll 45 patients.

Previously untreated extensive-stage SCLC patients, after signing the informed consent, will be screened and included if they meet the eligibility criteria. They will receive Sintilimab combined with chemotherapy (Carboplatin/Cisplatin + Etoposide) for 4 to 6 cycles, followed by maintenance therapy with Sintilimab until disease progression, death, intolerable toxicity, withdrawal of informed consent, initiation of new antitumor treatment, or other reasons for treatment termination as stipulated in the protocol. The early phase of this study is a safety lead-in period, observing the safety of 3 to 6 patients receiving first-line treatment with Sintilimab combined with chemotherapy (Carboplatin/Cisplatin + Etoposide): initially enrolling 3 patients and observing dose-limiting toxicities (DLTs) within the first cycle of the first medication, assessing the number of events, and if not more than one, the protocol will continue; otherwise, another 3 cases will be observed. During the safety lead-in period, if there are more than 4 DLT events, the dosage of the combined medication will be adjusted, and the study will proceed according to the adjusted dosage. The maximum duration of Sintilimab use is 2 years. After resistance to immunotherapy, the investigator will determine different treatment plans based on different resistance patterns, such as local therapy + immunotherapy.

The study uses RECIST v1.1 for clinical tumor imaging evaluation, which is performed every 6 weeks (±7 days) according to the patient's clinical condition; after 24 weeks of medication, it can be once every 9 weeks (±7 days) until disease progression, initiation of new antitumor treatment, withdrawal of the Informed Consent Form (ICF) by the subject, or death, or up to 2 years of Sintilimab use. Subjects who experience disease progression for the first time, if their clinical condition is stable and the investigator determines that they can continue to receive medication in this study, will do so. Patients who discontinue treatment for reasons other than disease progression still need to undergo imaging evaluation after stopping treatment according to the protocol until the next event occurs (initiation of new antitumor treatment, disease progression, withdrawal of ICF by the subject, or death).

After the study treatment is terminated, subjects will undergo safety follow-up (30±3 days after the last medication) and survival follow-up (every 90±7 days).

The primary endpoint of this study is the 1-year PFS rate, defined as the proportion of patients without disease progression at one year.

Sample Size

Based on previous research data, the 1-year PFS rate for patients with extensive-stage SCLC receiving first-line chemotherapy does not

Estimation

exceed 5.4%. It is estimated that the use of first-line Sintilimab combined with chemotherapy can increase the 1-year PFS rate of patients to 15%. Through sample size calculation, with α =0.05 (one-sided test), Power=80%, and assuming a dropout rate of 10%, using the One-Sample Logrank Test, a total of 45 patients are required to be enrolled.

- (1) Age: ≥18 years and ≤75 years old;
- (2) A confirmed diagnosis of extensive-stage small cell lung cancer (SCLC) by pathological examination (including histology or cytology);
- (3) Previously untreated patients who have not received any systemic antitumor therapy;
- (4) Asymptomatic patients with brain metastases, or those with brain metastases that have been treated and maintained a clinically stable condition for at least one month, and have not used corticosteroids and anticonvulsant medications for at least one month prior to entering the study;
- (5) Measurable lesions (as defined by RECIST 1.1, the long diameter of the tumor lesion on CT scan is ≥10mm, the short diameter of the lymph node lesion on CT scan is ≥15mm, the scan slice thickness is no more than 5mm, and the measurable lesions have not received local treatments such as radiotherapy or cryotherapy);

Inclusion Criteria

- (6) ECOG PS: 0-2;
- (7) Estimated life expectancy ≥3 months;
- (8) Adequate hematological function, defined as an absolute neutrophil count of ≥1.5×10^9/L, a platelet count of ≥80×10^9/L, and hemoglobin ≥90g/L (without transfusion or correction with G-CSF or other hematopoietic growth factors within 7 days);
- (9) Adequate liver function, defined as a total bilirubin level \leq 1.5 times the upper limit of normal (ULN) and levels of aspartate aminotransferase (AST) and alanine aminotransferase (ALT) \leq 2.5 times ULN for all patients;
- (10) Adequate renal function, defined as a creatinine clearance rate ≥50ml/min (Cockcroft-Gault formula);
- (11) Adequate coagulation function, defined as an international normalized ratio (INR) or prothrombin time (PT) ≤1.5 times ULN; if the subject is receiving anticoagulant therapy, as long as the INR/PT is within the range specified for the anticoagulant medication, it is acceptable;

- (12) For female subjects of childbearing age, a negative urine or serum pregnancy test should be presented within 3 days prior to the first administration of the study drug; if the result of the urine pregnancy test cannot be confirmed as negative, a blood pregnancy test is required;
- (13) If there is a risk of conception, male and female patients must use effective contraception (i.e., a method with a failure rate of less than 1% per year) and continue to do so for at least 180 days after discontinuation of the trial treatment; Note: If abstinence is the subject's usual lifestyle and the preferred method of contraception, abstinence can be accepted as a contraceptive method;
- (14) The subject voluntarily participates in this study, signs a written informed consent form before any trial-related procedures are implemented, and has good compliance and cooperation with follow-up.
- (1) Currently participating in an interventional clinical study treatment, or having received treatment with other investigational drugs or devices within 4 weeks prior to the first dosing;
- (2) Having previously received the following therapies: anti-PD-1, anti-PD-L1, or anti-PD-L2 agents, or drugs targeting another costimulatory or co-inhibitory T-cell receptor (e.g., CTLA4, OX-40, CD137);
- (3) Having received traditional Chinese medicine with anticancer indications or drugs with immunomodulatory effects (such as thymosin, interferons, interleukins, etc.) within 2 weeks prior to the first dosing, or having undergone significant surgical treatment within 3 weeks prior to the first dosing;

Exclusion Criteria

- (4) Presence of clinically significant active hemoptysis, active diverticulitis, abdominal abscess, gastrointestinal obstruction, and peritoneal metastasis requiring clinical intervention;
- (5) Having undergone organ or hematopoietic system transplantation;
- (6) New York Heart Association class II-IV congestive heart failure, poorly controlled and clinically significant arrhythmias;
- (7) Known hypersensitivity to the active ingredients of Sintilimab, Etoposide, Cisplatin, or Carboplatin, or any excipients;
- (8) A history of active autoimmune diseases requiring systemic treatment (e.g., the use of disease-modifying drugs, corticosteroids, or immunosuppressants) within 2 years prior to the first dosing. Replacement therapies (such as thyroid hormone, insulin, or

- physiological doses of corticosteroids for adrenal or pituitary insufficiency) are not considered systemic treatment;
- (9) Patients requiring long-term systemic use of corticosteroids. Patients who require intermittent use of bronchodilators, inhaled corticosteroids for COPD, asthma, or local injection of corticosteroids can be enrolled;
- (10) Failure to fully recover from toxicities and/or complications caused by any intervention (i.e., ≤Grade 1 or returned to baseline, excluding fatigue or alopecia);
- (11) A diagnosis of other malignant tumors within 5 years prior to the first dosing, excluding those with radical treatment of skin basal cell carcinoma, skin squamous cell carcinoma, and/or in situ carcinoma that has been radically excised. If other malignant tumors or lung cancer were diagnosed more than 5 years before dosing, pathological or cytological diagnosis of recurrent or metastatic lesions is required;
- (12) A history of non-infectious pneumonia requiring corticosteroid treatment within 1 year prior to the first dosing or the presence of non-infectious pneumonia;
- (13) Active infection requiring treatment or the use of systemic antiinfective drugs within one week prior to the first dosing;
- (14) Known mental illness or drug abuse that may affect compliance with trial requirements;
- (15) Known history of human immunodeficiency virus (HIV) infection (i.e., positive for HIV 1/2 antibodies), known syphilis infection (positive for syphilis antibodies), active pulmonary tuberculosis;
- (16) Untreated active hepatitis B; Note: Hepatitis B subjects who meet the following criteria are also eligible for inclusion: The HBV viral load must be <1000 copies/ml (200 IU/ml) or below the lower limit of detection prior to the first dosing, and subjects should be closely monitored for viral reactivation throughout the entire study. During chemotherapy treatment, subjects receive anti-HBV treatment to prevent viral reactivation. For subjects who are anti-HBc (+), HBsAg (-), anti-HBs (-), and have an undetectable HBV viral load (-), prophylactic anti-HBV treatment is not required, but close monitoring for viral reactivation is necessary.
- (17) Subjects with active HCV infection (positive for HCV antibodies and HCV-RNA levels above the lower limit of detection);
- (18) Have received live vaccinations within 30 days prior to the first dosing; Note: Intramuscular inactivated viral vaccines for seasonal

influenza are permitted; however, live attenuated influenza vaccines administered nasally are not allowed; (19) Have a medical history, disease, treatment, or laboratory abnormalities that may interfere with the trial results, prevent full participation in the study, or that the investigator deems participation in the study is not in the best interest of the subject; (20) Have local or systemic diseases caused by non-malignant tumors, or secondary reactions to cancer that could lead to increased medical risks and/or uncertainty in the evaluation of life expectancy. (21) The investigator deems the subject unsuitable for inclusion. 1. Sintilimab: 100 mg/10 ml, 200 mg, administered via intravenous infusion on Day 1, Q3W (every 3 weeks) 2. Carboplatin: AUC 5 mg/ml/min, administered via intravenous infusion on Day 1, Q3W Study 3. Cisplatin: 20 mg/vial, 75 mg/m^2, administered via intravenous Medication infusion on Day 1, Q3W and Administration 4. Etoposide: 100 mg/5 ml, 100 mg/m², administered via intravenous Method infusion on Days 1-3, Q3W Continue until disease progression, death, intolerable toxicity, withdrawal of informed consent, initiation of new antitumor treatment, or termination for other reasons specified in the protocol, with a maximum duration of Sintilimab use of 2 years. Therapeutic Efficacy Assessment: - The investigator will assess therapeutic efficacy according to RECIST 1.1. The evaluation includes progression-free survival (PFS), 1-year PFS rate, overall survival (OS), and objective response rate (ORR). Safety Assessment: **Evaluation** - The incidence, relationship to the study medication, and severity of Criteria all adverse events (AEs), treatment-related adverse events (TRAEs), immune-related adverse events (irAEs), and serious adverse events (SAEs); - The number of subjects who discontinue the study due to the aforementioned adverse events: - Changes in vital signs, physical examination results, and laboratory results before, during, and after the study treatment.

The statistical analysis primarily employs programming calculations using the SPSS statistical analysis software. Statistical tests utilize one-tailed and two-tailed tests, with a P-value less than or equal to 0.05 considered to indicate a statistically significant difference, and the confidence interval adopts a 95% confidence level.

Statistical Methods

Progression-free survival (PFS) and overall survival (OS) are estimated using the Kaplan-Meier method to determine the median values and their 95% CI, and survival curves are plotted. The objective response rate (ORR, which equals complete response [CR] plus partial response [PR]) and its 95% CI are calculated. Quality of life scores are compared with baseline examination values, and paired t-tests or signed rank tests are used to compare within-group differences before and after.

Safety evaluations are primarily based on descriptive statistical analysis, listing the incidence and severity of adverse events in this trial, and describing abnormal changes in laboratory test indicators, vital signs, and physical examination findings.

Visitation Flowchart

Table 1: Study Visit Process Chart

Phase	Screening Phase		nt Phase (Ever ne treatment of C2/D1		Maintenance Treatment Phase (Every 21 days as one treatment cycle)	Safety Visit ¹⁵	Survival Follow-up Visit ¹⁶
Day	-28~-1	1	22	21 (n-1) +1		30 days post- final drug administration	Every 90 days
Time Window (Days)	NA	+3	±3	±3	±3	±7	±7
General Study							
Process							
Informed Consent ¹	Х						
Inclusion/Exclusion	X						
Criteria							
Demographic/Medical History/History of Previous Lung Cancer Treatment ²	Х						
Concomitant	Х	Х	Х	Х	Х	Х	
Medications							
Vital Signs ³	Х	Х	Х	Х	Х	Х	
Body Weight/Height ⁴	Х	Х	Х	Х	Х	Х	
Physical Examination	Х	Х	Х	Х	Х	Х	
12-Lead	Х		Х	Х	Х	Х	
Electrocardiogram							
(ECG) ⁵							
Echocardiogram	Х						
(Echo)							
Cardiac Enzyme	Х		Х		Х		
Profile							
Survival Status							Х
Laboratory							
Assessment							

Phase	Screening Phase	Treatment Phase (Every 21 days as one treatment cycle)		Maintenance Treatment Phase (Every 21 days as one treatment cycle)	Safety Visit ¹⁵	Survival Follow-up Visit ¹⁶	
		C1/D1	C2/D1	Cn/D1			
Day	-28~-1	1	22	21 (n-1) +1		30 days post- final drug administration	Every 90 days
Time Window (Days)	NA	+3	±3	±3	±3	±7	±7
Complete Blood Count (CBC) 6	X		X	X	Х	Х	
Blood Biochemical Tests ⁶	Х		Х	Х	Х	Х	
Urine Routine Examination ⁶	Х		X	Х	Х	Х	
Pregnancy Test ⁷	Х						
Thyroid Function 8	Х		Х	Х	X	Х	
Viral Antibody Testing (HIV, HBV, and HCV) ⁹	Х						
Safety Monitoring							
and Survival							
ECOG PS score							
Adverse Event Assessment 10	Х	Х	Х	Х	X	Х	X
Subsequent							Х
Antitumor Therapy							
Quality of Life							Х
Questionnaire							
Therapeutic Efficacy							
Assessment							
Tumor Imaging	Х			Х	Х	Х	
Assessment 14							
Drug Administration							
Sintilimab		Х	Х	Х	Х		

Phase	Screening Phase	Treatment Phase (Every 21 days as one treatment cycle)			Maintenance Treatment Phase (Every 21 days as one treatment cycle)	Safety Visit 15	Survival Follow-up Visit ¹⁶
		C1/D1	C2/D1	Cn/D1			
Day	-28~-1	1	22	21 (n-1) +1		30 days post- final drug administration	Every 90 days
Time Window (Days)	NA	+3	±3	±3	±3	±7	±7
Cisplatin/Carboplatin plus Etoposide		Х	Х	Х			
Biomarker							
Archived/Fresh Tumor Tissue 13	Х						
Blood ¹⁴		X		X			

Notes:

- 1. The signing of the Informed Consent Form (ICF) should be conducted before any operations stipulated by the protocol.
- 2. History of prior lung cancer treatment: All treatments for lung cancer, including chemotherapy, radiation therapy, and surgical treatment.
- 3. Vital signs include: body temperature, pulse, respiratory rate, and blood pressure.
- 4. Height measurement is only conducted during the screening phase. The weight of the subject is measured before each dosing. If the subject's weight fluctuates by less than 10% compared to the baseline weight (the day of the first dose of study treatment), the baseline weight is used to calculate the dosage of the chemotherapy drug. Otherwise, the actual dosage is calculated based on the weight on the day of the scheduled dosing.
- 5. The 12-lead electrocardiogram (ECG) is conducted during the screening phase, treatment phase, and safety follow-up.
- 6. The complete blood count includes: red blood cell count (RBC), hemoglobin (HGB), hematocrit (HCT), white blood cell count (WBC), platelet count (PLT), and white blood cell differential [lymphocytes, neutrophils, monocytes, eosinophils, basophils]. Blood biochemistry includes: liver function [Total Bilirubin (TBIL), Direct Bilirubin (DBIL), Alanine Aminotransferase (ALT), Aspartate Aminotransferase (AST), Gamma-Glutamyl Transferase (γ-GT), Alkaline Phosphatase (ALP), Albumin (ALB), Total Protein (TP), Lactate Dehydrogenase (LDH), Creatine Kinase (CK)], kidney function [Urea or Blood Urea Nitrogen (BUN), Creatinine (Cr)], blood electrolytes (Na, K, Cl, Mg, Ca, P), amylase, and fasting blood glucose (FBG). Urine routine examination includes: pH, Urinalysis White Blood Cells (UWBC), Urine Protein (UPRO), Urinalysis Red Blood Cells (URBC), Glucose (UGLU), and specific gravity. Subjects with urine routine showing protein ≥2+ during the

screening phase should undergo a 24-hour urine protein quantification. Conducted within 7 days before the first dosing of the study drug in the screening phase, within 3 days before the dosing of the study drug at the beginning of the second cycle, and during the safety follow-up.

- 7. Women of childbearing age will undergo urine or serum pregnancy tests within 3 days before the first dosing in the screening phase and during the safety follow-up. If the urine pregnancy test result cannot be confirmed as negative, a serum pregnancy test will be conducted, and the serum pregnancy test result will prevail.
- 8. Thyroid function tests are conducted within 28 days before the first dosing, within 3 days before the dosing of the study drug at the beginning of the second cycle, and during the safety follow-up. In the screening phase, T3/FT3, FT4, and TSH are checked; from the second cycle, only TSH is checked, and if abnormal, other thyroid function indicators may be considered. During the study treatment process, it is not necessary to wait for the results of this test before proceeding with the study drug administration.
- 9. Include HIV and HCV antibody tests, as well as hepatitis B panel tests (HBsAg, HBsAb, HBcAb, HBeAg, HBeAb), which must be completed within 28 days before the first dosing. 10. AE and laboratory test safety assessments will be conducted according to CTCAE v5.0. The definition, recording, relatedness judgment, severity judgment, reporting timelines, and management of AEs and SAEs refer to the description in Section 8 of the protocol.
- 11. The quality of life questionnaire includes EORTC QLQ-C30 (V3.0 Chinese version), which is assessed on the day of the first dosing (before dosing), at each imaging assessment, and during safety follow-up. If an unplanned imaging assessment is conducted, the quality of life questionnaire should also be administered concurrently.
- 12. Tumor assessment includes RECIST 1.1 assessment. It is assessed by the investigator and must include the cervical, thoracic, abdominal, and pelvic regions. According to the RECIST v1.1 criteria, baseline (within 28 days before the first dosing), an assessment is conducted every 6 weeks (±7 days); after 24 weeks of medication, an assessment can be done every 9 weeks (±7 days) until disease progression, initiation of new antitumor treatment, withdrawal of ICF by the subject, or death. Subjects who experience disease progression for the first time, if their clinical condition is stable, the investigator will determine whether they can continue treatment.
- 13. Subjects are required to provide archived or fresh tumor tissue samples during the screening phase.
- 14. Subjects are required to provide a 10 ml whole blood sample for the detection of tumor biological markers at the following time points: before the first dosing, during the treatment phase before the next treatment and imaging assessment, and when disease progression is confirmed.
- 15. Safety follow-up will be conducted 30±3 days after the last dosing or before the initiation of new antitumor treatment, whichever occurs first. All AEs occurring before the safety follow-up visit should be recorded until they are resolved to grade 0-1 or baseline levels, or the investigator deems further follow-up is unnecessary for justified reasons (whichever occurs first). SAEs occurring within 90 days after the last dosing or before the subject starts new anticancer treatment (whichever occurs first) should be followed up and recorded.

16. Survival follow-up: Conducted every 90 days (±7 days) after the safety visit, which can be done via telephone.						

Contents

1 RE	ESEARCH BACKGROUND	18
	1.1 DISEASE BACKGROUND	18
	1.2 RISK AND BENEFIT ASSESSMENT	22
2 RE	ESEARCH PURPOSE	22
	2.1 Main Purpose	22
	2.2 Secondary Purposes	22
	2.3 EXPLORATORY PURPOSES	22
3 ST	TUDY DESIGN	22
	3.1 Overall Design	22
	3.1.1 Sample Size Estimation	23
4 ST	FUDY POPULATION	23
	4.1 Inclusion Criteria	23
	4.2 Exclusion Criteria	25
	4.3 RESTRICTIONS DURING THE STUDY PERIOD	26
	4.3.1 Pregnancy	26
	4.3.2 Fertility	26
	4.3.3 Lactation	27
	4.4 CRITERIA FOR SUBJECT DISCONTINUATION OF TREATMENT/WITHDRAWAL FROM TH	E STUDY
•••		
	4.4.1 Discontinuation of Study Treatment	28
	4.4.2 Withdrawal from the Study	28
	4.4.3 Clinical Criteria for Early Termination of the Study	29
5 ST	TUDY MEDICATION AND OTHER TREATMENTS	29

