4.4.3 Clinical Criteria for Early Termination of the Study

The study will be prematurely terminated if the following criteria are met:

- The quality and quantity of data recorded are inaccurate or incomplete.
- Compliance with the study protocol and regulatory requirements is poor.

The incidence or severity of adverse drug reactions in this study or other studies suggests potential harm to the health of subjects. If the sponsor decides to no longer provide the study drug, adequate notice will be given to allow for appropriate adjustments to the subject's treatment.

5 Study Medication and Other Treatments

For all other study treatment cycles, the medication may be administered within 3 days before or after the first day of the planned weekly cycle at the discretion of the investigator for management reasons.

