5.2 Dose Adjustments

5.2.1 Dose Adjustments for Sintilimab

- The dose of Sintilimab is not to be adjusted throughout the study. The principles for withholding and permanently discontinuing Sintilimab are outlined in Table 4. If an administration delay occurs during a 3-week cycle of Sintilimab treatment, all future dosing dates will be postponed to ensure that the dosing intervals between cycles of Sintilimab treatment are within 21 ± 3 days. Sintilimab-related adverse events are typically immune-related AEs. For pauses in administration due to immune-related AEs, based on the type and severity of the AE, corticosteroid treatment can be administered to alleviate to grade 1 or 0, and then the corticosteroids can be tapered over more than 4 weeks, after which the administration can be resumed.

Table 4: Dose Adjustment Scheme for Sintilimab-Related Immune Adverse Events

Immune-Related Adverse	Severity	Dose Adjustment
Events		
	Grade 2	Hold treatment ^a
Pneumonia	Recurrent Grade 2, Grade	Permanent discontinuation
	3 or 4	
	Grade 2 or 3 Diarrhea or	Hold treatment ^a
Diarrhea/Enterocolitis	Enterocolitis	
Diairriea/Enterocollis	Grade 4 Diarrhea or	Permanent discontinuation
	Enterocolitis	
Dermatitis	Grade 3 Dermatitis	Hold treatment ^a
Demanus	Grade 4 Dermatitis	Permanent discontinuation
	For subjects with normal	Hold treatment ^a
	baseline ALT, AST, or TBIL,	
	Grade 2 elevation of AST,	
	ALT, or TBIL; For subjects	
	with baseline AST, ALT, or	
Hepatitis	TBIL > ULN, an increase of	
riepatitis	AST, ALT, or TBIL \geq 50%	
	(meeting Grade 2	
	requirements) and duration	
	< 7 days	
	For subjects with baseline	Permanent discontinuation
	ALT, AST, or TBIL within	

	normal limits, Grade 3 or	
	Grade 4 elevation of AST,	
	ALT, or TBIL; for subjects	
	with baseline AST, ALT, or	
	TBIL > ULN (Upper Limit	
	of Normal), an increase in	
	AST, ALT, or TBIL by ≥50%	
	(meeting the criteria for	
	Grade 3 or Grade 4) and	
	duration ≥7 days	
	Grade 2	Hold treatment
pituitary inflammation	Grade 3 or Grade 4	Hold treatment or
		Permanent discontinuation
adrenal insufficiency	Grade 2	Hold treatment
	Grade 3 or Grade 4	Hold treatment or
		Permanent discontinuation
hyperthyroidism	Grade 3 or Grade 4	Hold treatment or
		Permanent discontinuation
hypothyroidism	Grade 2-4	Continue treatment
Type 1 diabete	Grade 3 hyperglycemia	Hold treatment
	Grade 4 hyperglycemia	Hold treatment or
		Permanent discontinuation
renal insufficiency	Grade 2 or Grade 3	Hold treatment ^a

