Prolonged duration (i.e., failure to respond quickly after symptomatic treatment and/or brief interruption of infusion); symptoms recur after initial improvement; hospitalization required due to other clinical sequelae (such as renal impairment, pulmonary infiltration).

Grade 4:

Life-threatening; requiring pressor agents or ventilatory support.

medications may include but are not limited to:

- Epinephrine
- Intravenous fluids
- Antihistamines
- Nonsteroidal antiinflammatory drugs (NSAIDs)
- Acetaminophen
- Analgesics
- Oxygen
- Pressor agents
- Corticosteroids

Closely monitor the patient's vital signs according medical to indications until the investigator deems the subject's condition stable. Hospitalization may be required.

In the event of an allergic reaction, administer epinephrine immediately.

The subject should permanently discontinue further study drug treatment.

Appropriate emergency equipment should be available in the ward, and a physician should be readily accessible during the administration period. For further information, please refer to the Common Terminology Criteria for Adverse Events (CTCAE) version 5(http://ctep.cancer.gov).

5.2.3 Dose Adjustment of Chemotherapy Drugs:

If the investigator confirms that the toxic reaction is mainly caused by a single chemotherapy drug, a reduction in the dose of that single drug is acceptable; if it is not possible to clearly attribute the toxic reaction to two or more drugs, a reduction in all drugs considered relevant may be made simultaneously. If the administration of chemotherapy is delayed during a treatment cycle of every 3 weeks, all future dosing dates will be postponed to ensure that the dosing interval between chemotherapy cycles is 21±3 days. The chemotherapy cycle and the Sintilimab cycle should be synchronized as much as possible by adjusting the allowed window period. The maximum allowed period of discontinuation for chemotherapy drugs is 6 weeks from the last chemotherapy interval; if the requirements for chemotherapy administration cannot be met after more than 6 weeks, the chemotherapy should be permanently discontinued.

The following are the different dose levels for chemotherapy drugs. If a further dose reduction is required after reducing by two dose levels, discontinue the chemotherapy drug.

Table 6: Dose Adjustment Levels for Chemotherapy Drugs

	Original	One Dose Level	Two Dose Levels
	Dose	Reduction	Reduction
Etoposide	100mg/m ²	75 mg/m ²	50 mg/m ²

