8.7 Management of Drug-Related Toxicity

The sponsor conducts regular safety audits at the trial level during the conduct of the trial. Detailed information including the frequency of audits and the types of data reviewed will be recorded in a separate trial-level safety audit plan.

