Summarize by group the proportion and frequency of subjects who violated the expected dosing regimen, the proportion of subjects whose study drug dosage was within 80% to 120% of the protocol-specified dose, and the proportion of subjects who completed the study and different treatment cycles.

10 Quality Assurance and Quality Control

Research personnel must be physicians who have received clinical trial training and work under the guidance of senior professionals.

Pre-trial inspections of clinical wards must meet standardized requirements to ensure that resuscitation equipment is complete.

It is recommended that professional nursing staff administer medication to subjects, understand in detail the medication intake, and ensure subject compliance.

Research centers must strictly follow the study protocol and accurately record case report forms.

Monitors should follow standard operating procedures, supervise the conduct of clinical trials, confirm that all data recording and reporting are correct and complete, all case report forms are entered correctly, and are consistent with the original data, ensuring that the trial is conducted in accordance with the clinical study protocol.

In the event of a Serious Adverse Event (SAE), it must be promptly reported to all research units, and if necessary, the study should be temporarily suspended.

11 Ethical, Regulatory, and Administrative Principles

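### The safety lead-in changes the dose only above 4 DLT events in at most 6 patients, so 3 of 3 or 4 of 6 affected patients lead to no study-level dose change

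*Protocol*

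**What the plan says.** The lead-in appears only in the Study Design row of the Protocol Summary; section 3.1 does not mention it. Three patients are treated and first-cycle DLT events are counted. The first decision is "if not more than one, the protocol will continue; otherwise, another 3 cases will be observed". The only other decision, for the lead-in as a whole, is "if there are more than 4 DLT events, the dosage of the combined medication will be adjusted", after which the study goes on at the adjusted dosage. The text names neither the drug to be adjusted nor the size of the step.

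Section 5.2.1 says "The dose of Sintilimab is not to be adjusted throughout the study" and notes that "Sintilimab-related adverse events are typically immune-related AEs". Table 4 handles those events by holding or stopping sintilimab in the individual patient. Reduced dose levels exist only for the chemotherapy, in section 5.2.3 and Table 6 ("The following are the different dose levels for chemotherapy drugs").

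Three other provisions concern safety for the study as a whole. Section 4.4.3 lists as a ground for early termination: "The incidence or severity of adverse drug reactions in this study or other studies suggests potential harm to the health of subjects". Section 8.7 says "The sponsor conducts regular safety audits at the trial level during the conduct of the trial", with details in a separate plan. Section 10 provides that after a serious adverse event, "if necessary, the study should be temporarily suspended". None of these three gives a DLT count or refers to the lead-in.

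**The concern.** The first step treats two events in three patients as enough of a signal to observe three more. The second step then tolerates up to four events without a stated response. An expansion that can end at 4 of 6 with nothing changed does little to gate the dose for the remaining patients of the planned 45.

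The unit makes this worse. Five events in one patient trigger an adjustment, while four patients with one event each do not. What matters for dosing the next patients is mainly how many patients cannot tolerate the first cycle, and an event count does not measure that directly.

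The action is also unclear. Adjusting the dosage of the combination suggests that any component may change, but section 5.2.1 fixes sintilimab. Only the chemotherapy can be reduced, and the lead-in text does not say so.

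At stake is the only numerical toxicity check at study level in the document at hand.

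**Working it through.** The protocol states no operating characteristics for the lead-in, so there is no figure to reproduce.

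**Inputs.** From the Protocol Summary: 3 patients first; continue at 0 or 1 event; otherwise add 3; adjust at 5 or more events. Assumed: the true proportion p of patients with a first-cycle DLT, from 10% to 80%; patients independent; and one of two models for events. Model A has at most one DLT per patient. Model B has Poisson events with mean λ = −ln(1−p) per patient, so that p is still the proportion affected. These are two models and not bounds, because clustering of events within patients is unknown.

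**Observed proportion at the trigger.** Under model A the trigger needs 5 of 6 patients (83%; exact 95% interval 36% to 99.6%). The highest result that passes is 4 of 6 (67%; 22% to 96%).

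**Present rule, model A.** With X1, X2 ~ Bin(3, p):

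- P(adjust) = P(X1 ≥ 2 and X1+X2 ≥ 5) = 6p⁵(1−p) + p⁶
- P(2 to 4 events after 6) = P(X1 ≥ 2) − P(adjust)

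At p = 0.50: 6/64 + 1/64 = 7/64 = 10.9%; then 50.0% − 10.9% = 39.1%.

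**Present rule, model B.** With E1, E2 ~ Poisson(3λ):

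- P(stop at 3 patients and continue) = (1−p)³(1+3λ)
- P(2 to 4 events after 6) = (1−p)⁶(4.5λ² + 18λ³ + 37.125λ⁴)
- P(adjust) = 1 minus both

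At p = 0.50, λ = 0.6931: 0.3849 and 0.2613, leaving 0.3537.

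| True rate | Adjusts, A | Adjusts, B | Ends with 2–4 events, A | Ends with 2–4 events, B |
|---|---|---|---|---|
| 10% | <0.1% | <0.1% | 2.8% | 4.0% |
| 20% | 0.2% | 1.0% | 10.2% | 13.5% |
| 33% | 1.7% | 8.2% | 23.8% | 25.6% |
| 50% | 10.9% | 35.4% | 39.1% | 26.1% |
| 60% | 23.3% | 58.1% | 41.5% | 17.9% |
| 67% | 35.8% | 73.3% | 38.7% | 11.1% |
| 80% | 65.5% | 93.2% | 24.1% | 2.1% |

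Under A the 2-to-4 outcome is most frequent near 60%. Under B it is similar at 33% and 50% and then falls quickly, because the event count itself often reaches 5.

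**Patient trigger alone** (expand at 2 of 3; adjust once 3 patients are affected):

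P(adjust) = P(X1=3) + P(X1=2)·P(X2 ≥ 1). At p = 0.50: 8/64 + 21/64 = 29/64 = 45.3%.

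At 10%, 20%, 33%, 50%, 67% and 80% this gives 0.8%, 5.5%, 18.9%, 45.3%, 72.9% and 89.3%.

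**Both triggers, expansion still at two or more events.** Under A nothing changes, because 5 events mean 5 patients. Under B, the expanded lead-ins that still do not adjust are those with at most 2 affected patients and at most 4 events. Counting how 2, 3 or 4 events can fall on six patients gives:

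P(adjust) = 1 − (1−p)³(1+3λ) − (1−p)⁶(4.5λ² + 8λ³ + 5.625λ⁴)

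At p = 0.50: 1 − 0.3849 − 0.0957 = 51.9%. At 10%, 20%, 33%, 67% and 80% it gives 0.9%, 6.0%, 21.3%, 81.2% and 94.8%.

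**The case against.** The strongest reply is that this is not a dose-finding study. Sintilimab is given at a fixed dose, the chemotherapy is called standard, and the background describes an approved PD-L1 inhibitor plus etoposide and carboplatin. A one-sided trigger means that below it the study continues, so the rule is lenient rather than incomplete. This largely stands: continuing is the natural reading of 2 to 4 events. But that reading is the problem, since it lets 4 of 6 affected patients pass.

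A reader might go further and infer that toxicity is unguarded. The documents do not support that. Tables 4 and 6 to 9 act in every patient, and sections 4.4.3, 8.7 and 10 allow action on the whole study. What they lack, in the text shown, is a DLT threshold. The separate safety audit plan named in section 8.7 is not at hand, so whether it holds one cannot be said.

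A reader might also infer that a conventional 3+3 rule is required. It is not. It would adjust 9.4% of the time at a true rate of 10% and 29.1% at 20%, a real cost in a 45-patient efficacy trial.

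Three further objections are sound. At true rates of 10% to 20% the 2-to-4 outcome is uncommon (2.8% to 13.5%). A patient count replacing the event count would, under Poisson events, act slightly less often than the present rule at 67% and 80% (72.9% against 73.3%, and 89.3% against 93.2%). And immune-related DLTs gain little, because sintilimab cannot be dose-adjusted.

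**Conclusion.** The point holds as a badly set rule, not as a missing safeguard. As written, the lead-in changes the dose only at 5 or more events. With one DLT per patient, neither 3 of 3 nor 4 of 6 affected patients reaches that. At a 33% true rate it adjusts in 1.7% to 8.2% of lead-ins across the two models, and at 50% in 10.9% to 35.4%. At very high rates the event count acts often if patients have several events each. If the true rate is 10% to 20%, the weakness is seldom exposed.

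The size depends on assumed rates, independence between patients and the event model, since the protocol states no expected rate. The reading of the rule does not depend on them: the threshold, the event unit and the bar on sintilimab dose changes are all in the text.

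**What to change.** Amend the lead-in paragraph as follows:

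- Count patients with at least one first-cycle DLT alongside the events.
- Keep the expansion to 6 at two or more events in the first 3 patients.
- Adjust as soon as 3 patients are affected: 3 of 3 adjusts at once, and 2 of 3 adjusts if any of the next 3 is affected.
- Keep the present trigger of more than 4 events as a second trigger. With expansion still based on events, every lead-in that adjusts today then also adjusts under the new rule, so it never acts less often.
- State that 2 of 6 affected patients continues, unless the event trigger is met.
- State that the adjustment is a one-level Table 6 chemotherapy reduction. Immune-related DLTs stay under the patient-level hold or stop rules of Table 4, so the change adds little for them.

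The cost is a text amendment. An unneeded adjustment occurs in 0.8% of lead-ins at a true rate of 10% and 5.5% at 20%, or 0.9% and 6.0% with both triggers under Poisson events. With one DLT per patient, expansion becomes slightly less frequent because 3 of 3 no longer waits (21.9% against 25.5% at 33%). Even so, at a 33% true rate the patient trigger leaves the dose unchanged about 81% of the time. A sponsor wanting more protection there could choose a 3+3 rule and accept more unneeded adjustments.
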